9.2.5.2 Exposure Assessment in Cases

In this section, operational definitions for identifying exposure should be described, including type of vaccine codes.

Exposure status will be identified in confirmed and probable cases. For this study, an indicator for each dose of <<COVID-19 vaccine product>> and date of vaccination will need to be identified for all cases. In the SCRI design, if multiple doses of vaccine are given during the study period, each individual dose will be evaluated separately. To the extent feasible, in the case of multidose vaccines, exposure information should be captured following hospital discharge to avoid bias due to the outcome impacting the observation period for exposure. If collecting exposure information after hospital discharge is not possible, the impact of this potential bias could be explored in a sensitivity analysis using Farrington’s pseudolikelihood method for censored, perturbed, or curtailed postevent exposures [7].

In the primary analysis, exposure will be based on a specific COVID-19 vaccine product; a secondary analysis will be conducted stratified by vaccine groupings defined by technology, platform, or components (e.g., mRNA, adenovirus backbone, protein recombinant vaccines, adjuvant). If the concern for a particular outcome is related to a specific product (as per data existing at the time of full protocol development), the analysis for the particular outcome will only be conducted for the specific product, and a combined analysis of products will not be conducted.

Exposure information will be obtained from pharmacy dispensing records, general practice records, immunisation registers, vaccination cards, medical records, and/or other secondary data sources. The availability and feasibility of data sources to obtain vaccination information will likely vary by jurisdiction. Depending on the data source, vaccines may be identified via Anatomical Therapeutic Chemical codes, nationally used codes, local codes, or free text. If vaccination cards are used, and if feasible, a sample of vaccine records could be validated against other sources such as medical records or health care provider questionnaire to confirm the vaccine product and date of vaccination.

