 - For persons who receive only one dose, define the risk and control intervals as 1 to 42 and 43 to 127 days after vaccination, respectively.
 - In the above scenarios, the control window could be placed even further in time from vaccination to incorporate a washout period between the risk and control intervals, as needed.
- If there is a short interval between doses of the vaccine but the risk interval is short, a dose-level analysis (treating each dose as a separate observation) could be conducted, but care must also be taken to ensure that the control interval does not overlap with the next dose. For example, suppose the vaccine is administered in two doses approximately 28 days apart, and the outcome of interest has a risk interval of 0 to 7 days. The control interval would need to end before 27 days after vaccination (e.g., 8-15 days) to ensure that there is no overlap of the control interval of the first dose with the risk interval of the second dose.

If the outcome affects the likelihood of a subsequent vaccination after the first dose, the impact of this potential bias could be explored in a sensitivity analysis using Farrington’s pseudolikelihood method for perturbed, censored, or curtailed observation periods for postevent exposures [7].

CCO Design

If the CCO design is used, an exposure window preceding the event will be selected to reflect the period during which exposure to COVID-19 vaccination is hypothesised to trigger the adverse event of interest. A single comparison window preceding the risk window will be selected to reflect the baseline prevalence of exposure; the comparison window should be selected independently of exposure status. Multiple comparison windows per case may also be considered but are not recommended because they may increase the potential for bias due to time-varying confounding and temporal trends in

exposure. By convention, the exposure window will index on the date of the adverse event, which will be time = 0. A washout period between the exposure and comparison windows can be implemented to avoid any carryover effects of the vaccine between the two windows.

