9.6.2 Measures of Association

If the SCRI is used, conditional Poisson regression (conditioned on the individual) will be used to estimate incidence rate ratios and 95% confidence intervals for each outcome, with logarithm of time in each interval as the offset. If the CCO is used, conditional logistic regression (conditioned on the individual) will be used to estimate odds ratios and 95% confidence intervals for each outcome.

For the SCRI and CCO, time-varying confounders will be adjusted for in regression models. If applicable, in the SCRI, age and calendar time may be categorised into several categories, or treated as polynomial functions, with or without the use of splines in regression models. Both unadjusted and adjusted incidence rate ratios, by site and pooled across all sites, will be reported.

If the vaccinated case-coverage design is used, a logistic regression model will be fit for each AESI under study using separate summarised data sets. The data set for each AESI under study will have one record per risk set (i.e., case), with the outcome indicating whether vaccination occurred in the case's exposure or comparison window. The logarithm of the expected odds (i.e., logit) of vaccination inside the exposure window will be entered into the model as an offset term. For each case, this expected probability of vaccination inside the exposure window will be obtained from the reference population, as described in Annex 3. The model will include only an intercept with no covariate, with the following general form.

$$\text{Logit}(p_1) = \text{logit}(p_0) + \beta_0,$$

where p_1 is the observed probability of vaccination inside the exposure window among cases, p_0 is the expected probability of vaccination inside the exposure window among cases (based on vaccination data in the reference population), β_0 is the intercept; by exponentiating this coefficient, one obtains an odds ratio describing the association between vaccination and the outcome of interest occurring inside the risk interval.

Of note, the logistic regression model drops all cases for whom the expected probability of vaccination inside the exposure window is 0 or 1 (i.e., either everyone or no one is vaccinated inside the risk interval amongst the reference population), as these cases are noninformative.

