9.6.4 Subgroup Analysis

If relevant to specific adverse events, the presence of effect modification by relevant variables (dose number, age at vaccination, specific comorbidities, concomitant vaccinations) will be assessed by adding an interaction term between vaccination and the effect modifier of interest to regression models for the CCO and SCRI designs. Effect modification will be assessed in the vaccinated case-coverage design by adding the potential effect modifier as a covariate to the regression model.

Subgroup analysis will be performed by strata of effect modifiers of interest as relevant. For the vaccinated case-coverage design, subgroup analysis will require that the at-risk-stratum for calculating the expected odds of vaccination be redefined based on the different subgroups.

[The study investigator(s) should describe subgroups motivated by the current understanding of the study outcomes in this section.]

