Control windows may be before or after vaccination and are typically a fixed length between individuals, although they are not required to be the same length as the risk window. This control period serves as an estimate of the baseline incidence. Unlike the traditional cohort study, the SCRI design does not censor follow-up at an event. These designs are well suited to study single or multiple exposures and independent recurrent events or rare non-recurrent events. However, if an event is recurrent but each occurrence is not independent of one another (e.g., stroke, myocardial infarction), then the analysis should be limited to the first event.

In a hospital-based study, the SCRI design would be operationalised by first identifying patients who have been treated and/or diagnosed with the outcomes of interest at hospital sites (regardless of vaccination status). Among the cases, vaccinations and date of vaccinations would then be identified. This approach has important study design and methodological implications because only exposures that occur before the outcome will be available for analysis, unless it is feasible to collect exposure information following hospital discharge. A SCRI design with a pre-vaccination control interval could be considered if it is feasible to collect exposure information following hospital discharge, as

this would enable the inclusion of outcomes that occur before exposure; to use this approach, the outcome should not be a contraindication to exposure. The use of a pre-vaccination control interval would provide more timely results than a postvaccination control window, as data must fully accrue through the end of follow-up for each dose before it can be included in analyses. However, it is anticipated that information on exposures may not be available after hospital discharge to the end of the study period, as was the case in a proof-of-concept study conducted by the World Health Organization (WHO) Global Vaccine Safety: Multi Country Collaboration [21]. Therefore, subsequent discussion of the SCRI in this document will describe the use of a postvaccination control interval, which would not require collection of exposure information following hospital discharge.

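### Dose-level SCRI: 9.2.5.3 makes each dose its own observation but 9.6.2 conditions on the individual; if post-event doses go unrecorded, shared strata bias dose-specific and calendar-adjusted IRRs

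*Protocol*

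**What the plan says.** **Unit of observation.** Protocol 9.2.5.2 says of the SCRI that "if multiple doses of vaccine are given during the study period, each individual dose will be evaluated separately". Section 9.2.5.3 adds that, for short risk intervals, "a dose-level analysis (treating each dose as a separate observation) could be conducted". Its example has two doses about 28 days apart, risk days 0-7 and control days 8-15. It contrasts this with a person-level analysis that combines doses when the risk interval is long.

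**Model.** Section 9.6.2 gives one SCRI model for all variants: "If the SCRI is used, conditional Poisson regression (conditioned on the individual) will be used to estimate incidence rate ratios". Calendar time and age may enter it, and unadjusted and adjusted IRRs are both to be reported. Section 9.6.4 assesses dose number, a secondary objective in section 8, "by adding an interaction term between vaccination and the effect modifier of interest to regression models". It also mentions analyses within strata of the modifier. It does not mention a dose main effect.

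**What is known about doses.** Annex 3 says that "only exposures that occur before the outcome will be available for analysis, unless it is feasible to collect exposure information following hospital discharge". It then settles on a postvaccination control interval, "which would not require collection of exposure information following hospital discharge". Section 9.2.5.2 asks for post-discharge capture with multidose vaccines where feasible. Where it is not, 9.2.5.2 and 9.6.5 offer the pseudolikelihood method as an optional sensitivity analysis. Annex 3 also says that, for a multidose vaccine, the postvaccination control interval by itself deals with the bias. The same sentence goes on to offer further remedies, so a negation may have been lost.

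**The concern.** Suppose the 9.6.2 model is applied literally to dose-level data, so that a person's dose-1 and dose-2 windows form one stratum. If dose 2 is not recorded once an event has occurred, a case after dose 1 contributes only dose-1 windows. A case after dose 2 contributes the windows of both doses, always with the event in the later pair. The likelihood cannot tell this recording pattern from biology. It reads low risk around dose 1 and high risk around dose 2 or, if calendar time is in the model, a rising time trend that distorts the vaccination effect.

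At stake are the dose-number result and the adjusted any-dose IRR. Section 9.5 plans a common programme run at every site, so a wrong stratum identifier would be repeated everywhere and pooling would not dilute it.

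**Working it through.** **Inputs from the Protocol.** Risk window 0-7 and control window 8-15 (8 days each), doses 28 days apart (9.2.5.3); conditional Poisson by individual (9.6.2); vaccination-by-dose interaction (9.6.4); doses known only up to the event (Annex 3).

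**Assumptions not in the Protocol.** Constant baseline rate, no vaccine effect, exact 28-day spacing, every vaccinee receives dose 2 unless stated, first doses spread evenly over 120 days, calendar categories of 14 to 60 days, two-sided 5% tests.

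**1. The plan's own figure.** Table 3 gives 69 cases for relative incidence ρ = 2 with a share r = 0.5 of the time at risk. Use n = (1.96 + 0.8416√B)²/A, where p = ρr/(ρr + 1 − r), A = 2[p ln ρ − ln(ρr + 1 − r)] and B = (ln ρ)² p(1 − p)/A. Then p = 0.667, A = 0.1133, B = 0.943 and n = 68.1, which rounds up to 69. The other 14 cells also reproduce to within about 1.5 cases. Table 3 is not in question; 69 serves below as a realistic study size.

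**2. Dose-specific IRRs, individual strata.** Let a and b be the IRRs for doses 1 and 2. With no effect, each dose has equal numbers of cases, half in each window. Let s be the share of dose-1 cases whose later dose 2 is recorded. A stratum with dose 1 only has denominator a + 1; a stratum with both doses has S = a + b + 2. The score equations per dose are:

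- dose 2: 1/2 = (1 + s) b/S, so b = (a + 2)/(1 + 2s)
- dose 1: 1/2 = (1 − s) a/(a + 1) + (1 + s) a/S

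| Post-event dose 2 recorded | Equation for a | Dose 1 | Dose 2 |
|---|---|---|---|
| none (s = 0) | a² + a − 1 = 0 | 0.618 | 2.618 |
| half (s = 0.5) | 2a² + a − 2 = 0 | 0.781 | 1.390 |
| all (s = 1) | a = 1 | 1.00 | 1.00 |

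With none recorded and lower dose-2 uptake, the pair is 0.667 and 2.667 at 80% uptake, and 0.758 and 2.758 at 50%. The result therefore does not depend on universal uptake.

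**3. False findings with 69 cases** (4,000 simulated studies, Wald tests). None recorded: false dose-2 harm in 77% and a false dose interaction in about 95%. Half recorded: 19% and 34%.

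**4. Calendar-adjusted any-dose IRR, individual strata** (true value 1.00).

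| Category width | None recorded | Half recorded |
|---|---|---|
| 60 days | 1.21 | 1.07 |
| 30 days | 1.45 | 1.14 |
| 14 days | about 1.8 | about 1.18 |

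**5. Where the bias vanishes.** With one stratum per person-dose, every IRR above is 1.00. The same holds with individual strata plus a dose-period main effect, although with no post-event recording that coefficient diverges. The unadjusted any-dose IRR is 1.00 throughout, because both doses have the same risk-to-control ratio.

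**The case against.** The strongest reply is that the Protocol already intends the dose as the unit. Section 9.2.5.2 evaluates each dose separately, 9.2.5.3 contrasts dose-level with person-level analysis, and 9.6.4 allows analysis within strata of a modifier. A separate model per dose, restricted to that dose's windows, is unbiased even when conditioned on the individual, because each individual then has only one dose in the model. On this view, the 9.6.2 wording is a generic description of self-controlled models. The worst case also needs the interaction to be fitted without a dose main effect, which 9.6.4 does not require.

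Much of this stands. A reader might infer that the Protocol prescribes the biased analysis, or leaves pseudolikelihood as the only safeguard. The text supports neither. The dose-level analysis is one of several possible approaches in a template. Post-discharge dose capture is requested where feasible, and Annex 3 also suggests placing control intervals where vaccination is unlikely. Table 1 makes pseudolikelihood a recommendation, not an option, when the outcome censors exposure. Section 9.2.5.5 advises against equally spaced calendar categories, so the calendar figures are only illustrative. The SCRI is the primary design in one of the four Table 2 scenarios.

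One part does not stand. This is not detail left to an analysis plan: 9.6.2 states the conditioning unit, and 9.6.4 puts dose number into that model. No section says that the stratum changes for the dose-level option.

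**Conclusion.** The sections on unit of observation and on model conflict. This should be corrected. Followed literally, 9.6.2 and 9.6.4 produce a false dose-2 signal from the recording pattern alone: 0.62 and 2.62 at worst, 0.78 and 1.39 with half of the post-event doses recorded. The calendar-adjusted any-dose IRR is inflated to about 1.2-1.8, or 1.07-1.18 with half recorded. These sizes rest on the example windows, a constant baseline, no dose main effect (for the dose-specific figures) and assumed calendar categories.

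A reader might go further and infer that all multidose SCRI results are invalid. They are not. The unadjusted any-dose IRR with equal dose effects, sites that capture all post-event doses, and per-dose models on their own windows are unaffected. Nor is it established that investigators would choose the shared stratum; the Protocol simply does not rule it out.

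**What to change.** 1. In 9.6.2 add: *In the dose-level SCRI, the conditioning stratum is the person-dose, comprising that dose's own risk and control windows, and not the individual.*
2. In 9.6.4 fit the dose-number interaction with these strata. Alternatively, require a dose-period main effect, so that the control days of the two doses are not a common reference. Person-dose strata are simpler, because the main effect has no finite estimate when no post-event doses are recorded.
3. Reconcile 9.2.5.2, 9.2.5.3, 9.6.2 and 9.6.4 with each other, and with the Annex 3 statement that the postvaccination control interval alone resolves the bias for multidose vaccines.
4. Keep the pseudolikelihood method for the person-level analysis with long risk intervals, where doses are combined and person-dose strata are not available.

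The cost is a sentence or two and a different stratum identifier in the common programme. What is given up is the comparison of event rates between doses within a person, which is the component that carries the bias. The risk-versus-control contrast for each dose, and the comparison of those contrasts between doses, remain estimable.

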If the vaccine is administered in multiple doses, then each exposure code will be considered to be a separate instance of vaccination, provided that sufficient time has passed between the dates of the codes, based on the vaccine dosing schedule and taking into account the possibility that some persons may receive subsequent doses slightly earlier than indicated in the vaccine dosing schedule (for example: if the vaccine dosing schedule calls for two doses at least 28 days apart, then any code for vaccination that occurs fewer than 21 days after the first code would be excluded, under the assumption that any additional codes after the first code are duplicates of the same dose). If the vaccine is administered as a single dose, then only the first exposure code during the study period will be considered, which assumes that the remaining codes are errors.

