9.2.5.3 Risk and Control Windows

In this section, risk/exposure windows will be defined for <<adverse event>> in table format.

SCRI

If the SCRI is used, a risk window, in which person-time will be considered exposed, will be selected after vaccination to reflect the hypothesised period of increased risk of the outcome due to vaccination. By convention, the risk window will index on the date of vaccination, which will be time = 0. A postvaccination control window will be selected to estimate the baseline rate of the outcomes. The control window definition (length and timing relative to vaccination) will be the same across individuals and will balance the need to obtain adequate statistical power against the threats of bias due to loss to follow-up and time-varying confounding. A washout period following the risk window may be incorporated to avoid any carryover effects of the vaccine into the postvaccination unexposed person-time.

If multiple doses of vaccine are given during the study period, the risk and control windows of one dose must not overlap with the risk or control windows of a subsequent dose, based on the vaccine dosing schedule. Some possible approaches to define the control interval, depending on the length of the risk interval and spacing between doses of the vaccine, are provided below:

- If there is a short interval between doses of the vaccine and a long risk interval, it would be necessary to avoid overlap of the risk interval of one dose with the risk and/or control intervals of a subsequent dose; depending on the length of the risk interval and the spacing between doses, it may be necessary for the control interval to be positioned after the risk interval of the final dose. For example, suppose the vaccine is administered in two doses approximately 28 days apart, and the outcome of interest has a risk interval of 1 to 42 days. Conducting a dose-level analysis (i.e., considering each dose to be a separate observation), with a risk interval of 1 to 42 days following each dose could potentially lead to confounding of the first dose by receipt of the second dose, and vice versa. To address this, a person-level analysis could be conducted combining the risk intervals following each exposure, for example:
 - For persons who receive two doses, define the risk interval as 1 to 42 days after the first dose plus 1 to 42 days after the second dose. The control interval could then be defined as 43 to 127 days after the second dose.

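### The day-27 limit on the SCRI control interval (9.2.5.3) does not ensure non-overlap, because the dose-coding example in 9.2.5.2 accepts a second dose from day 21

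*Protocol*

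**What the plan says.** Three statements in the protocol bear on this point.

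- **The rule (9.2.5.3, SCRI).** For multidose vaccines, "the risk and control windows of one dose must not overlap with the risk or control windows of a subsequent dose", judged on the dosing schedule. The same section keeps the length and timing of the control window the same for all individuals.
- **The short-risk-interval example (9.2.5.3, SCRI).** Doses are about 28 days apart, the risk interval is days 0-7, and each dose is analysed as a separate observation. The text then says: "The control interval would need to end before 27 days after vaccination (e.g., 8-15 days) to ensure that there is no overlap".
- **The dose-identification example (9.2.5.2).** The text allows for second doses given somewhat early. For a schedule of at least 28 days it says that "any code for vaccination that occurs fewer than 21 days after the first code would be excluded". A code on day 21 or later therefore counts as a second dose.

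Section 9.2.5.3 also has a long-risk-interval example, with doses about 28 days apart and risk days 1-42. There the protocol leaves the dose-level analysis and says that "a person-level analysis could be conducted combining the risk intervals following each exposure". For two-dose persons the instruction is to "define the risk interval as 1 to 42 days after the first dose plus 1 to 42 days after the second dose", with control time on days 43-127 after the second dose.

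**The concern.** The day-27 limit is offered as a guarantee. It leaves one day of slack against a gap of exactly 28 days, whereas the dose-identification example leaves seven. An investigator who follows both sections could set a dose-1 control window of days 8-26 and accept a second dose on day 21. Days 21-26 would then be both dose-1 control time and dose-2 risk time.

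Section 9.2.5.2 evaluates each dose separately, so events caused by dose 2 would enter the dose-1 baseline. If the vaccine does raise the risk, that inflates the baseline and pulls the dose-1 rate ratio toward 1, the unwelcome direction in a safety study. The text offers no rescue by shortening the window person by person, because the window is fixed. The note to investigators in section 8 allows some sections' wording to be kept unchanged, so the example may well be copied.

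**Working it through.** **Inputs.** Dose 1 is on day 0 and dose 2 on day g. The dose-2 risk interval is days g to g+7 (risk days 0-7, 9.2.5.3). The latest control day allowed is 26 (9.2.5.3). The earliest accepted dose 2 is day 21 (9.2.5.2).

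**The plan's own figure.** At g = 28 the dose-2 risk interval is days 28-35, so the last non-overlapping control day is 27. A control interval ending on day 26 at the latest overlaps by 0 days, with one day to spare. The stated limit is correct for a gap of exactly 28 days, and also for 27.

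**Shorter gaps that 9.2.5.2 accepts.** Overlap of control days 8-26 with the dose-2 risk interval is max(0, 26 − g + 1) days:

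| Gap g (days) | Overlap, control 8-26 | Overlap, control 8-15 |
|---|---|---|
| 21 | 6 | 0 |
| 22 | 5 | 0 |
| 23 | 4 | 0 |
| 24 | 3 | 0 |
| 25 | 2 | 0 |
| 26 | 1 | 0 |
| 27 | 0 | 0 |
| 28 | 0 | 0 |

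**Effect on the dose-1 ratio, worst case.** Control days 8-26 are 19 days. If every dose 2 falls on day 21, 13 of these are clean and 6 are dose-2 risk days. Assume the same true ratio RI after either dose. The control rate is inflated by (13 + 6·RI)/19, and the estimate is RI divided by that factor.

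- RI = 2: (13 + 12)/19 = 1.316; 2/1.316 = 1.52.
- RI = 3: (13 + 18)/19 = 1.632; 3/1.632 = 1.84.
- RI = 1: the factor is 1, so there is no bias.

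**Milder cases.** The protocol gives no share of early doses; 25% is an assumption for illustration.

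- 25% with dose 2 on day 21, the rest at 27 days or more. RI = 2: 1 + 0.25 × 0.316 = 1.079, estimate 1.85. RI = 3: 1 + 0.25 × 0.632 = 1.158, estimate 2.59.
- 25% early, spread evenly over days 21-27. Mean overlap is (6+5+4+3+2+1+0)/7 = 3 days. RI = 2: 1 + 0.25 × 3 × 1/19 = 1.039, estimate 1.92. RI = 3: 1 + 0.25 × 3 × 2/19 = 1.079, estimate 2.78.

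**The person-level example.** At a 28-day gap the two risk intervals are days 1-42 and 29-70 after dose 1. They share days 29-42, which is 14 days. Counted once, the risk time is 42 + 42 − 14 = 70 days. The control interval starts after day 70, so no risk day is used as control. The protocol gives no total. Only if 84 days were entered in the offset of 9.6.2 would the ratio in two-dose persons be multiplied by 70/84 = 0.83.

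**The case against.** The strongest reply is that the short-interval example obeys the rule as written. The rule is judged on the dosing schedule, and at a 28-day gap there is no overlap. The window actually printed, days 8-15, is safe at every gap from 21 to 28 days; days 8-26 is a window that the limit allows but the protocol never proposes. The day-21 figure is itself an example, inside a rule for removing duplicate codes, and for doses at least 28 days apart rather than about 28. Annex 3 already advises placing control time where a further vaccination is very unlikely. All of this is optional template text.

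Most of that stands, and it limits the point to the general day-27 limit. It does not rescue the limit. The example's own premise of an approximate 28-day gap admits shorter gaps, section 9.2.5.2 expects them, and the sentence claims to ensure non-overlap.

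A reader might go further and infer that both multidose examples break the no-overlap rule, with the person-level example adding risk days up to 84. The documents do not support this. That example is the protocol's remedy for overlap: it drops the dose-level analysis because this "could potentially lead to confounding of the first dose by receipt of the second dose, and vice versa", and places control time after the last risk interval. It never states 84 days. Since the offset is time in each interval, and a person cannot accrue 84 days of follow-up in 70, merged person-time is the natural reading. Under that reading there is no bias.

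**Conclusion.** The point holds for the day-27 limit. Read with 9.2.5.2, it permits a dose-1 control window containing 1 to 6 days of dose-2 risk time for gaps of 26 down to 21 days, and so biases the dose-1 ratio toward 1 when a risk exists.

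The estimates of 1.52 for a true ratio of 2 and 1.84 for a true ratio of 3 are a worst case. They assume the longest control window allowed, every second dose on day 21, and the same true ratio after both doses. With a quarter of persons early (assumed), the estimates are 1.85 to 1.92 for a true ratio of 2 and 2.59 to 2.78 for a true ratio of 3. A control window ending by day 20, including the printed 8-15, carries no such bias. The dose-2 estimate and Table 3 are not affected.

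In the person-level example only the wording is loose. The factor of 0.83 is conditional on double counting, which the protocol does not prescribe, and would apply only to two-dose persons.

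**What to change.** In the short-risk-interval example of 9.2.5.3, replace the day-27 limit with one tied to the exposure definition: the control interval of a dose must end before the earliest day on which 9.2.5.2 accepts the next dose (before day 21 in this example, so the last control day is 20), as the same fixed window for all persons. Cutting control time at each person's actual second-dose date would not be a good substitute, because it conflicts with the fixed window that 9.2.5.3 requires.

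The cost is one sentence and at most 6 possible control days (days 8-20 are 13 days, against 19 for days 8-26). The printed 8-15 window needs no change.

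As a minor clarification, add to the person-level example that the combined risk time is the union of days 1-42 after each dose, each day counted once (70 days at a 28-day gap), and that this length enters the offset. It should be worded as a union rather than as one continuous span from the first dose to day 42 after the second. With a gap above 42 days, a continuous span would include days outside both risk intervals.
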